NCT03868631

Muscle growth and development following a 12-week resistance training program in men
and women consuming soy and whey protein supplements.

August 1, 2016

Methods

Participants

Two hundred eighty-two people responded to the screening survey online from August 2016 through January 2017. Most survey respondents did not meet inclusion requirements or failed to reply to an email invitation to come in for a baseline lab visit. Sixty-one participants were randomized for study participation. Participants were healthy, nonsmoking males and females with a body mass index (BMI) between 18.5 and 29.9, ages 18-35 years who were recreationally active but had not participated in structured weight training for at least the previous 12 months. Exclusion criteria included adherence to a vegetarian or vegan diet; having any chronic disease; use of tobacco products; current pregnancy or lactation, being within six months post-partum, or intention to become pregnant in the next 12 weeks; allergy to whey or soy; change in body weight more than ten pounds in the previous three months; and any musculoskeletal injury or condition that would preclude full participation in a new exercise program. All participants provided written informed consent before enrollment in the study. The study was approved by the Institutional Review Board of Arizona State University and is in compliance with the Declaration of Helsinki as revised in 1983.

Study design

A prospective, 2-group parallel-arm, randomized, double-blind study was conducted to compare the impact of soy or whey protein isolate supplements, matched for leucine content, on strength and lean body mass changes in response to resistance training. Enrolled participants were randomly assigned to receive either 19 grams of whey protein isolate or 26 grams of soy protein isolate daily. The varying amounts of protein supplement were chosen to ensure each contained two total grams of leucine. This amount of leucine was targeted for consumption as 10 grams of EAA (including ~1.8 g leucine) has been shown to be sufficient to maximally stimulate muscle protein synthesis (MPS) in young men and women, and that additional leucine (3.5 g) does not further augment MPS. Participants were stratified based on the baseline visit measurements for BMI, leg extension peak torque, and lean body mass, and randomly assigned to the treatment groups. Participants and all investigators except one were blinded to the group assignment; the investigators collecting and analyzing data were all blinded to group assignment. The investigator who knew group assignment remained uninvolved with data collection and assessment until the study was completed. Participants in both groups engaged in an identical supervised resistance training program, consisting of training on three nonconsecutive days per week for 12 weeks. Outcome measures (see below) were assessed prior to training, and after six and 12 weeks of training.

Dietary protocol

Participants were clearly instructed to maintain their usual diet and physical activity level throughout the duration of the study, which was encouraged during each training session. Three times during the study (baseline, midway through the study, and during the 12th week of the intervention) participants completed three-day food logs (two weekdays and one weekend day). Participants were instructed by a Registered Dietitian Nutritionist (RDN) on how to complete the food logs completely and of the importance in being detailed and accurate in their records, including brand names when possible and precise amounts of each food, beverage, and condiment. All diet records were entered into Food Processor SQL Nutrition and Fitness Software by ESHA Research, Inc. (version 10.11.0, Salem, OR, USA) by the same person to ensure standardization. Total kilocalories, grams of protein, and percent

contribution of macronutrients were compared within participants and between group means to evaluate if participants maintained the composition of their diets during the intervention.

Supplement protocol

Protein powder was measured to the nearest gram using a MyWeight KD-8000 digital food scale. Daily protein was measured into individual plastic bags, and all portions required for the 12-week study were provided at the outset along with a shaker bottle to all participants. Protein supplements were either whey protein powder isolate (Bongards, Chanhassen, MN) or soy protein powder isolate (DuPont, Wilmington, DE). Leucine content of the products was determined from the USDA Nutrient database for soy protein isolate and from an analysis by the manufacturer for whey protein isolate since a product-specific analysis was available. The protein supplement was provided to participants in powdered form. Participants were instructed to consume the protein supplement daily by mixing the protein supplement with water. Participants were permitted to mix a non-nutritive sweetener with their protein powder if they wished, but not with milk or any other food substances or calorie-containing beverages. On workout days, the trainer observed the participant consume the protein powder immediately after the exercise session for added accountability. On non-workout days, participants were instructed to consume the protein between meals rather than concurrently with other food. This was to ensure timing of consumption would be ideal for maximizing the 24-hour muscle protein synthesis rate.

Resistance training protocol

The resistance training program consisted of whole body progressive resistance exercise training. Participants completed three workouts per week, each separated by at least 48 hours. Each workout began with an easy, self-selected five-minute warmup on the treadmill, elliptical, or stationary bike. Each resistance training session consisted of barbell bench press, incline chest press using a barbell, leg press, seated leg curl, leg extension, lat pull down, upright row, and abdominal exercises. Participants rested for 1-2 minutes between each set. The first workout of the week was not intended to take participants to complete muscular failure. However, the other two workouts per week were intended to elicit complete voluntary muscular failure. One-repetition maximum weight lifted was recalculated during the first workout of weeks 1, 4, 7, and 10 for the bench press, leg press, and knee extensions. Weeks 1-6 entailed lifting three sets of 10 repetitions at 60% of participants' one-repetition maximum (1-RM) for all exercises on the first workout of the week. The second and third workouts entailed lifting three sets of about 10 repetitions at about 70% 1-RM for each exercise. The precise weight lifted was increased as needed in order for participants to be completely fatigued by about repetition 10. Weeks 7-12 consisted of the same exercises but at a higher intensity. The first workout of each week consisted of four sets of eight repetitions at 70% 1-RM. The second two workouts of the week consisted of four sets of eight repetitions at 80% 1-RM. Similar to weeks 1-6, the actual weight lifted was increased above 80% 1-RM if needed in order for the participants to be completely fatigued after about repetition eight. In order to be included in analyses, participants could not have missed an a prior cut off of more than three training sessions in 12-weeks (completed at least 92% of sessions).

Study outcomes.

The following testing protocol was conducted prior to training and after six and 12 weeks of training. The only exception was that height was only measured during the pre-training period. Participants arrived to the lab having been asked to not perform exercise for a minima of 24 hours prior to the visit.

Participants' height and weight were measured using a SECA directprint 284 digital measuring station. Body composition was assessed using dual x-ray absorptiometry (DXA) (Lunar iDXA, General Electric Company, East Cleavland, OH, USA) which was obtained after voiding the bladder and participants laying down for 15 minutes to normalize fluid shifts. All scans were completed by the same certified radiology technician. Muscle thickness of the vastus lateralis (VL) and vastus intermedius (VI) of the self-determined dominate leg was assessed after 15 minutes of rest using ultrasound (uSmart 3300, Terason, Burlington, MA) and with a 15-4 Mhz linear transducer. Images were captured at 56% of the length from the greater trochanter of the femur to the lateral epicondyle. Circumference of the leg at this location was also measured. Image analysis was carried out using publicly available software (ImageJ, National Institutes of Health, USA). For the analysis of muscle thickness, ImageJ was first calibrated using the visible depth scale on each image. Muscle thickness (MT) of the VL and VI were measured. Briefly, MT of the VL was measured as the perpendicular distance between the border of subcutaneous fat and muscle to the deep aponeurosis. MT of the VI was measured as the perpendicular distance between the superficial aponeurosis and the superficial border of the femur. At each site, combined MT of the visible muscles (VL+VI) was also examined, measured as the perpendicular distance between the subcutaneous fat and muscle border to the superficial border of the femur. To account for changes in MT across the field of view (FOV) in each image, MT measurements were made at three locations across the FOV, corresponding to 10%, 50%, and 90% from left to right (based on pixel width of FOV). Measurements at the three locations across the FOV were averaged into one composite MT measurement for a given muscle. Following assessment of body composition and muscle thickness, isokinetic muscle strength was determined for the leg extensors and leg flexors on an isokinetic dynamometer (Computer Sports Medicine Inc. (CSMi), Stoughton, MA, USA). Briefly, participants were secured to the dynamometer to avoid any unnecessary movement. Participant performed two sets of three repetitions (30s rest in-between sets) on their self-reported dominant leg at 60 degrees per second (d/s). Participants were encouraged to produce maximal effort during each repetition. Peak torque was taken as the highest peak torque for flexion and extension from any of the sets.

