NCT03868631

Official title: Muscle growth and development following a 12-week resistance training program in men and women consuming soy and whey protein supplements.

Date: August 1, 2016

Statistical analyses

Some outcomes were transformed using log10 transformation (lean body mass, peak torque for leg extensions, visceral adipose tissue (VAT), and bone mineral density) or square root transformation (peak torque for leg flexions) to achieve normality. Between-arm differences at baseline were compared using independent t-tests. Age was non-normal and thus baseline differences were assessed using a Mann Whitney U Test. Multilevel models for change (MLM) were used to determine differences between arms over time for study outcomes. Age, sex, and number of sessions missed were included as covariates. Study outcomes tested were total body mass; lean body mass; fat mass; body fat percent; bone mineral density; leg extension peak torque; leg flexion peak torque; and total kcal, carbohydrate, protein, and fat consumed. Time (categorical) and time by study arm interaction effects were examined. Time was also included as a random effect for the intercept to improve model fit and to account for individual differences in change over time. Lean body mass and subcutaneous adipose tissue models failed to converge when including the number of sessions missed as a covariate (fixed effect); therefore, this variable was removed from the model for these two outcomes. Data shown in Tables 3-5 reflect multi-level modeling with all participants who started the training (N=31 whey, 30 soy). All analyses were conducted using IBM SPSS Statistics version 23.

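### Diet maintenance is assessed only by tests of difference with no tolerance, so a non-significant result could be read as maintenance without showing it

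*Protocol*

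**What the plan says.** Under Dietary protocol the Protocol records the instruction: "Participants were clearly instructed to maintain their usual diet and physical activity level throughout the duration of the study". Each participant kept a food log covering three days at baseline, midway and in week 12. Energy, grams of protein and the percent contribution of the macronutrients then "were compared within participants and between group means to evaluate if participants maintained the composition of their diets during the intervention".

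The SAP (Statistical analyses) lists "total kcal, carbohydrate, protein, and fat consumed" among the outcomes. For all outcomes it says: "Multilevel models for change (MLM) were used to determine differences between arms over time for study outcomes", and "Time (categorical) and time by study arm interaction effects were examined". The models use everyone who started training, 31 on whey and 30 on soy.

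The supplement portions differ by design (Protocol, Study design): "Enrolled participants were randomly assigned to receive either 19 grams of whey protein isolate or 26 grams of soy protein isolate daily".

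Neither document gives a tolerance for dietary change, a confidence-interval criterion, a significance level, or an SD for intake or its change. Neither says whether the study supplement is entered in the logs.

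**The concern.** The Protocol's question is whether diet stayed the same. The method named answers a different one: whether a difference can be detected. A non-significant time or time-by-arm effect may mean that diets were stable, or only that the logs were too variable to tell. Without a tolerance or an interval, the noisier the logs, the easier it is to reach a reassuring result.

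At stake is how a soy-whey difference, or its absence, in lean mass and strength is interpreted. A reader will want to know how large an arm difference in background protein or energy is still compatible with the data, and the planned tests do not say.

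There is also a mismatch of measure. The Protocol asks about composition and names macronutrient percentages. The SAP's list, which gives no units, reads most naturally as amounts eaten. Energy and protein match across the documents, but percent of energy has no clearly named analysis.

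**Working it through.** The plan has no power or precision figure for diet to reproduce. The check asks what the planned tests could detect.

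**From the documents.** Group sizes are 31 and 30. The difference in isolate portion is 26 − 19 = 7 g/day.

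**Assumed.** Two-sided 5% tests, 80% power, complete logs from all 61, and an SD of change in three-day mean protein of 20 to 40 g/day, with 10 shown as a favourable case. Simple t-tests on change from baseline to one later visit stand in for the three-visit multilevel model.

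**Formulas.**
- Standard error of the arm difference = SD × √(1/31 + 1/30) = 0.256 × SD.
- 95% half-width = t(59; 0.975) × 0.256 × SD = 2.001 × 0.256 × SD = 0.512 × SD. This is also the largest observed difference that stays non-significant.
- Arm difference detectable with 80% power (noncentral t, 59 df) = 0.729 × SD.
- Drift common to both arms, paired, n = 61: detectable with 80% power = 0.365 × SD.
- Drift within one arm, n = 30: 0.529 × SD.

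**Protein, g/day.**

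| SD of change | 95% half-width, arm difference | Detectable arm difference | Power for a true 7 g arm difference | Detectable common drift | Detectable one-arm drift |
|---|---|---|---|---|---|
| 10 | 5.1 | 7.3 | 77% | 3.6 | 5.3 |
| 20 | 10.2 | 14.6 | 27% | 7.3 | 10.6 |
| 30 | 15.4 | 21.9 | 15% | 10.9 | 15.9 |
| 40 | 20.5 | 29.2 | 10% | 14.6 | 21.2 |

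For SD 20 to 40 the detectable arm difference is 14.6/7 = 2.1 to 29.2/7 = 4.2 times the portion difference. Common drift is 7.3/7 = 1.0 to 14.6/7 = 2.1 times it.

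**Energy.** With an assumed SD of change of 400, 500 or 600 kcal/day, the same factors give detectable arm differences of 292, 365 and 438 kcal/day, and detectable common drifts of 146, 182 and 219 kcal/day.

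**Could 7 g/day serve as a tolerance?** Even with an observed difference of zero, a 95% interval fits inside ±7 only if 0.512 × SD < 7, that is SD < 13.7 g/day. Across SD 20 to 40 such a rule would always fail.

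**The case against.** The strongest reply is that neither document says a non-significant result will be reported as maintenance. The Protocol says the values were compared and the SAP says the effects were examined. That is correct: the reading is an inference from the absence of any other criterion, so the criticism is of what the plan leaves open.

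A reader might also infer that a large dietary drift would go unnoticed. The figures do not support this. A common drift of 14 g/day in protein would be detected with about 95% power at SD 30 and 77% at SD 40. If the supplement is counted in the later logs and not at baseline, a rise of roughly 19 to 26 g/day (powder weight) is built in. A 19 g rise would be detected with about 95% power even at SD 40, so the time test would tend to signal a change.

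The 7 g/day yardstick is fairly challenged too. It is grams of isolate, not of protein, and it follows deliberately from leucine matching. Nothing in the documents shows that 7 g, or 15 to 29 g, of background protein would alter the conclusions. It helps as a scale but not as a pass mark.

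Finally, allocation was randomised and double-blind, so drift common to both arms does not by itself bias soy against whey, and diet was also managed by instruction and encouragement. This limits the consequence. It does not turn a test of difference into evidence of sameness.

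**Conclusion.** The point holds in limited form. The plan's only stated check on diet is a set of tests of difference, and a non-significant result from them would not show that diets were maintained or equal. If the SD of change in protein is 20 to 40 g/day, an arm difference has to reach about 15 to 29 g/day to be detected with 80% power; at SD 10 it is about 7 g/day. Common drift is detected at about 7 to 15 g/day over the same SD range. All of these rest on an SD the documents do not give and on complete logs.

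The documents do not support saying that a difference far above 7 g/day would pass. It could pass between arms at the larger SDs, and at SD 20 a true 14 g/day arm difference is already detected with 77% power. Nor do they support saying that the trial has declared diet maintained on this basis, or that the comparison of strength and lean mass is invalid. The effect is on interpretation of that comparison.

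**What to change.** From the same multilevel models, report the mean change in each arm and the soy-whey difference in change, mid-study and at week 12, each with a 95% confidence interval. Do this for energy, grams of protein and percent of energy from each macronutrient, the last being the composition measure the Protocol names. State the number of logs behind each estimate and whether the supplement is counted in them. If it is counted, say so beside the protein results, because a time effect and an arm difference are then partly built in.

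In the text, say only that changes larger than the interval limits are excluded. Do not claim maintained or equal diets from non-significance, and do not use 7 g/day as a pass/fail tolerance. Because the SAP already describes fitted models and refers to results tables, a tolerance chosen now could not credibly be presented as set in advance; intervals avoid that difficulty.

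The cost is SAP and report wording plus model runs for percent of energy, on data already entered. No trial procedure changes. The downside is that the trial may be unable to claim that diet was maintained.

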NCT03868631

Official title: Muscle growth and development following a 12-week resistance training program in men and women consuming soy and whey protein supplements.

Date: August 1, 2016

Statistical analyses

Some outcomes were transformed using log10 transformation (lean body mass, peak torque for leg extensions, visceral adipose tissue (VAT), and bone mineral density) or square root transformation (peak torque for leg flexions) to achieve normality. Between-arm differences at baseline were compared using independent t-tests. Age was non-normal and thus baseline differences were assessed using a Mann Whitney U Test. Multilevel models for change (MLM) were used to determine differences between arms over time for study outcomes. Age, sex, and number of sessions missed were included as covariates. Study outcomes tested were total body mass; lean body mass; fat mass; body fat percent; bone mineral density; leg extension peak torque; leg flexion peak torque; and total kcal, carbohydrate, protein, and fat consumed. Time (categorical) and time by study arm interaction effects were examined. Time was also included as a random effect for the intercept to improve model fit and to account for individual differences in change over time. Lean body mass and subcutaneous adipose tissue models failed to converge when including the number of sessions missed as a covariate (fixed effect); therefore, this variable was removed from the model for these two outcomes. Data shown in Tables 3-5 reflect multi-level modeling with all participants who started the training (N=31 whey, 30 soy). All analyses were conducted using IBM SPSS Statistics version 23.

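### The week 12 time-by-arm contrast is an unadjusted difference in change; adjusting for each outcome's own baseline costs almost nothing and may sharpen it, by an amount the documents do not fix

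*SAP*

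**What the plan says.** The Protocol (Study design) has outcomes measured before training and at weeks 6 and 12, with randomisation stratified on baseline BMI, leg extension torque and lean mass.

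The SAP (Statistical analyses) states:

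- Model: "Multilevel models for change (MLM) were used to determine differences between arms over time for study outcomes".
- Effects tested: "Time (categorical) and time by study arm interaction effects were examined".
- Covariates: "Age, sex, and number of sessions missed were included as covariates".
- Random part: "Time was also included as a random effect for the intercept".
- Other stated use of baseline: "Between-arm differences at baseline were compared using independent t-tests".
- Scale: "Some outcomes were transformed using log10 transformation (lean body mass, peak torque for leg extensions", among others.
- Population for the results tables: "multi-level modeling with all participants who started the training (N=31 whey, 30 soy".

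It states no baseline covariate, no equality constraint on the baseline arm means and no covariate-by-time term. It does not list the levels of time. With a model for change and three measurement times, treating baseline as the first response is the natural reading.

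**The concern.** A reader who sees a covariate list may take the arm comparison to be adjusted. With complete visits it is not: the contrast is relative to baseline but makes no use of how well baseline predicts the later value, and testing baseline differences separately adjusts nothing. At stake is the width of the interval on the soy-whey difference in a trial of 61 people, for which the needed data are already in hand.

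**Working it through.** **Inputs.** From the documents: 31 whey and 30 soy, three visits, the terms listed above. Not in the documents, so assumed over a range: rho, the baseline-to-follow-up correlation, and k, follow-up SD divided by baseline SD. The SAP states no precision or power figure to reproduce.

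**1. What the contrast is.** Categorical time plus time by arm leaves all six arm-by-visit means free (rank 6; a model with equal baseline arm means has rank 5). With complete visits, the fitted mean for arm a at visit t is ybar(a,t) − b·xbar(a), where x holds the person-level covariates. In week 12 minus baseline, b·xbar(a) cancels whatever b is, leaving the raw difference in mean change. Generalised least squares with 31 + 30 people confirmed this:

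- The discrepancy was below 1e-14 under random-intercept, random-intercept-plus-slope and arbitrary unstructured covariance.
- The SE was the same with and without covariates (0.1984, 0.2530 and 0.5713 for the three structures).
- A mixed-model fit to one simulated data set gave −0.10691 (SE 0.14418) both with and without age, sex and sessions missed. Forcing equal baseline means did change it, to −0.11862 (SE 0.13577).

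Covariates interacted with time would not cancel, but the SAP states no such terms.

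**2. Precision, correct covariance.** With baseline SD s0 and follow-up SD s1, the variances per unit of (1/31 + 1/30) are:

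- change: s0² + s1² − 2·rho·s0·s1
- adjusted: s1²(1 − rho²)
- their difference: (s0 − rho·s1)², never negative and zero where rho·k = 1

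The SE ratio is sqrt[(1 − rho²)k² / (1 + k² − 2·rho·k)], which is sqrt((1 + rho)/2) at k = 1. Large-sample change in SE:

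| rho | 0.5 | 0.7 | 0.8 | 0.9 | 0.95 |
|---|---|---|---|---|---|
| k = 1 | −13.4% | −7.8% | −5.1% | −2.5% | −1.3% |
| k = 0.9 | −18.3% | −13.3% | −11.2% | −10.0% | −11.1% |
| k = 1.25 | −5.5% | −1.0% | 0 | −2.5% | −9.9% |

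For log10 outcomes a common percentage gain adds a constant, so k = 1 is a reasonable reference case (an assumption). If the adjusted test has 80% power, the unadjusted test has Phi(2.80·ratio − 1.96) = 68 / 73 / 76 / 78 / 79% across the k = 1 row, before any balance from stratification.

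**3. Small-sample cost.** Estimating one slope multiplies the SE by sqrt(1 + 1/57) = 1.009. At k = 1 the net change is −12.6 / −7.0 / −4.3 / −1.7 / −0.4%, then +0.1% at rho 0.97 and +0.6% at 0.99. Break-even is rho = 2·57/58 − 1 = 0.966. Null simulation (20,000 runs, simple randomisation) agrees: the adjusted/change variance ratio was 0.761, 0.911, 0.990 and 1.012 at rho 0.5, 0.8, 0.95 and 0.99. Both estimates were unbiased, with type I error 0.048–0.050.

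**4. Outcomes that are stratifiers.** The documents do not describe the strata, so median splits in blocks of 4 were assumed (4,000 runs, k = 1). Own-baseline adjustment cut the true SD by 6.0 / 2.7 / 1.3 / 0.7 / 0.2% over rho 0.5–0.95. The unadjusted contrast's reported SE against its true SD was 0.2557 v 0.2327 at rho 0.5, 0.1985 v 0.1855 at 0.7 and 0.1611 v 0.1599 at 0.8. Part of the benefit is therefore a less conservative reported SE.

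**5. If only a random intercept is fitted.** Assume unit SDs and correlations of 0.9 between adjacent visits and 0.8 from baseline to week 12.

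- True change variance: 2(1 − 0.8) = 0.40.
- Model value: 2·(0.2 + 0.2 + 0.4)/6 = 0.267.
- Multiplying by (1/31 + 1/30) = 0.0656 gives a reported SE of 0.132 against a true 0.162, a ratio of 0.816 and type I error of about 0.11.
- Correct adjusted SE: sqrt(0.36·0.0656) = 0.154, which is narrower than the truth for the change contrast but wider than the SE reported.

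**6. Missing visits.** With 20% and 40% assumed week 12 dropout, the constrained-baseline model kept variance ratios of 0.79–0.98 over rho 0.5–0.95. A completers-only baseline-adjusted model reached 1.03–1.05 at rho 0.9–0.95 with 40% dropout.

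**The case against.** A repeated-measures model with time by arm is an accepted analysis of a randomised trial, and nothing in the documents promises baseline adjustment. That stands: this is a suggestion about efficiency, and no passage is contradicted.

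The gain may be nil where it matters most. Five of the eleven outcomes listed in the SAP are body mass, lean mass, fat mass, fat percent and bone density. Over 12 weeks in a mixed-sex sample, correlations above 0.95 are plausible for these (an assumption), and the equal-SD gain there is about 1% or less. Lower correlations are more plausible for the food-log outcomes (also an assumption), but those check that diet was maintained rather than compare strength and lean mass. This also stands, and it is why the point ranks low.

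Three stronger readings are tempting, and the documents support none of them:

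- **That leaving out baseline biases the comparison or inflates false positives.** It does neither; the difference in mean change is unbiased under randomisation.
- **That the SAP's error rate is about 0.11.** This needs a random-intercept-only fit and decaying correlation. The random-effects sentence is ambiguous and no correlations are given, so it is a condition on the SE comparison and not a finding.
- **That the stratifiers should also become covariates.** As main effects in the present three-visit model they would cancel like the others. Added to own baseline with age and sex, they widened the simulated SE by up to about 3% at rho 0.9–0.95 (k = 1) and up to about 4% where rho·k = 1, when they predicted nothing further.

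**Conclusion.** The point holds as a minor efficiency improvement. On the natural reading, and with complete visits, the week 12 contrast is the unadjusted soy-whey difference in mean change. Own-baseline adjustment is never less precise in large samples and has a ceiling cost of about 1% in SE at N=61, reached only above rho of about 0.966 with equal SDs or near rho·k = 1.

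The benefit cannot be sized from the documents. It runs from nothing to more than 10% of the SE, and the upper end needs rho near 0.5 or a follow-up SD clearly below the baseline SD. For lean mass and leg extension torque the true-precision gain is about 6% to 0.2% under the assumed strata.

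All of these SE comparisons assume a correctly specified within-person covariance. Without that, a narrower interval cannot be promised.

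**What to change.** For each outcome, on the SAP's transformed scale, do one of the following:

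- **Preferred:** keep all three visits and constrain the baseline arm means equal. With equal variances this gives the same SE ratios as the k = 1 row (0.866 to 0.987), and it keeps all 61 participants.
- **Alternative:** model the week 6 and week 12 values with own baseline, by time, as covariate. This drops anyone with no follow-up value.

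Use an unstructured within-person covariance (six parameters for three visits), which also settles the ambiguity over the random effects. Leave out sessions missed: it is counted after randomisation and would no longer cancel. That also removes the term the SAP links to its fitting problem ("Lean body mass and subcutaneous adipose tissue models failed to converge when including the number of sessions missed as a covariate"). Do not add the stratifiers. Age and sex may stay as main effects; if they predict nothing beyond own baseline, the simulated SE was about 1% wider at rho 0.95 with equal SDs and 2.1–2.5% wider where rho·k = 1.

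Report the adjusted week 12 soy-whey difference with its 95% interval. Label it post hoc, because the SAP already describes model fits and refers to results tables.

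The cost is a change of SAP wording and a re-run on data already collected. Convergence of the new model cannot be judged from the documents.

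### On the natural reading of the SAP, age and sex are main effects, which adjust the soy-whey difference in gains hardly at all; covariate-by-time terms would do so

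*SAP*

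**What the plan says.** The SAP (Statistical analyses) fits multilevel models to compare the arms over time. On covariates it says "Age, sex, and number of sessions missed were included as covariates". On the effects of interest it says "Time (categorical) and time by study arm interaction effects were examined". No covariate-by-time term is mentioned. The one covariate whose role is spelled out is sessions missed: two models "failed to converge when including the number of sessions missed as a covariate (fixed effect"), and it was then dropped from them. The random part is described as "Time was also included as a random effect for the intercept to improve model fit".

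The Protocol (Study design) has outcomes that "were assessed prior to training, and after six and 12 weeks of training", so there are three visits. On allocation it says "Participants were stratified based on the baseline visit measurements for BMI, leg extension peak torque, and lean body mass". Sex is not listed as a factor, although men and women were both enrolled (Protocol, Participants). The SAP analyses 31 whey and 30 soy participants. Lean mass, extension torque, visceral fat and bone density are analysed on the log10 scale, and flexion torque on the square-root scale. No transformation is listed for body mass, fat mass, body fat percent or diet.

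**The concern.** The question the models answer is whether gains differ between soy and whey, which is a contrast of changes. Age and sex do not vary usefully within a person over 12 weeks. Entered as main effects, they explain differences in level between people but give men and women, and younger and older participants, the same modelled gain. A reader told that the models included age and sex would suppose that the soy-whey difference in gains was protected against an imbalance in either. On this specification it largely is not. Sessions missed, if entered as one total per participant, has the same limit.

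At stake is the point estimate for the allocation that occurred: if gains differ by sex on the analysed scale and the arms differ in their share of men, part of the observed contrast reflects sex. Some precision may also be lost.

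**Working it through.** The documents contain no power calculation or effect size, so there is no planned figure to reproduce. The check is algebra, then simulation under stated assumptions.

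**1. Cancellation.** Let the mean for arm g at visit t be μ(g,t) + βx, with x constant within a person. With complete visits and an arm main effect, the fitted cell mean is

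μ̂(g,t) = Ȳ(g,t) − β̂·x̄(g).

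The term β̂·x̄(g) is the same at every visit, so

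[μ̂(S,12) − μ̂(S,0)] − [μ̂(W,12) − μ̂(W,0)] = [Ȳ(S,12) − Ȳ(S,0)] − [Ȳ(W,12) − Ȳ(W,0)],

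and β̂ has gone. This holds for any within-person covariance, so the unclear random-effects wording does not change the result for the estimate.

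**2. What a sex imbalance contributes.** If p is the share of men in an arm and G the mean gain by sex, the contribution to the contrast is

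(p_soy − p_whey) × (G_men − G_women), on the analysed scale.

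**3. Simulation.** From the documents: 31 versus 30 participants, three visits. Assumed: 20/31 men on whey and 12/30 on soy, 12-week gain 2.0 in men and 1.0 in women, no true arm effect, between-person SD 4, residual SD 1. Random-intercept REML fits were used, with 200 runs per setting. The formula predicts (12/30 − 20/31) × 1.0 = (0.400 − 0.645) × 1.0 = −0.245. Mean 12-week time-by-arm estimates (mean SE):

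| Dropout | No covariates | Age and sex main effects | Plus sex-by-time and age-by-time |
|---|---|---|---|
| 0% | −0.248 (0.370) | −0.248 (0.370) | −0.009 (0.374) |
| 20% | −0.286 (0.412) | −0.285 (0.411) | −0.036 (0.418) |
| 35% | −0.206 (0.449) | −0.206 (0.448) | 0.029 (0.461) |

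With complete visits the main effects changed nothing in any run. With dropout, the mean absolute change in a single run was 0.019 (maximum 0.070) at 20% and 0.026 (maximum 0.108) at 35%. Only the interaction terms brought the contrast close to its true value of zero. When men and women were given equal gains, the mean contrast was 0.004.

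**4. Common-baseline variant.** The SAP does not mention an arm main effect. If the arms are constrained to share a baseline mean, the main effects do move the estimate, from −0.297 to −0.238 with complete data, but the part due to sex-specific gains remains.

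**5. Role of the scale.** Take levels of 55 in men and 40 in women and a 3% gain in both (assumed). On the raw scale the gains are 55 × 0.03 = 1.65 and 40 × 0.03 = 1.20, a difference of 0.45. On the log10 scale both are log10(1.03), the difference is 0, and nothing passes through.

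**6. Plausible range.** For assumed imbalances of 0.05 to 0.20 and gain differences of 0.25 to 1.0 units, the contribution runs from 0.05 × 0.25 = 0.0125 to 0.20 × 1.0 = 0.20 units. Against the simulated SE of 0.370 that is 0.03 to 0.54 SE.

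**7. How likely a large imbalance is.** If 30 of 61 are men and allocation ignores sex, the hypergeometric distribution gives an SD of 0.13 for the difference in shares and a probability of 0.13 for a gap of 20 points or more. If allocation is stratified at the lean-mass median (assumed sex separation 12 to 15 kg, within-sex SD 7 to 6 kg), the SD falls to 0.10 to 0.08 and the probability to about 0.06 to 0.02.

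**The case against.** The strongest reply is that the SAP is a one-paragraph summary which never says that the covariates were main effects only. That stands as a caution: the reading is inferred from the fact that one interaction is named and no other. It is still the natural reading.

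Several stronger conclusions are tempting, and the documents do not support them.

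- A reader might infer that the adjustment does nothing at all. That is exact only with complete visits and an arm main effect. The extent of missing follow-up is not stated, and with dropout or a common baseline the estimate does move, though not by enough to remove the sex component.
- A reader might infer that any sex imbalance carries over in full. It is multiplied by the sex difference in gain on the analysed scale, and it vanishes for a log10 outcome if percentage gains are equal.
- A reader might infer that the comparison is biased. Under randomisation, chance imbalance is part of sampling error. The issue is conditional bias for the allocation that occurred.
- A reader might infer that large sex imbalance is likely because sex was not a stratification factor. Lean mass and extension torque were factors and are plausible proxies for sex. The 24.5-point gap in the simulation is deliberately large.
- A reader might expect a clear gain in precision. The approximation √(1 + 0.25·d²/s²) − 1, with assumed gain difference d of 0.5 to 1.5 and within-sex SD of change s from 2.0 to 1.2, gives 1% to 18%. The simulated refit showed no gain (0.370 against 0.374), and the SAP's random-effects structure is unclear.
- A reader might infer that the trial cannot report gains for men and women. Nothing prevents descriptive means by sex.

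The convergence failures also count against simply enlarging every model, and the fix has to allow for them.

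**Conclusion.** The point holds in a limited form. Read naturally, the SAP's age and sex adjustment is close to inert for the contrast the trial tests, and sessions missed shares that limit if it is one total per person. This rests on the inferred main-effects specification. The cancellation itself is algebra, confirmed by simulation.

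The consequence is conditional bias and possible loss of precision. Its actual size is unknown because the inputs are not in the documents; the ranges above rest on assumed values. Nothing here shows that an imbalance occurred or that a conclusion would change. The change is worth making because it uses data already collected, acts on the contrast being tested and is inexpensive.

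**What to change.** In the SAP (Statistical analyses), add sex-by-time and age-by-time terms to the outcome models. Keep time by arm, averaged over sex, as the test. Do not describe a main-effects model as adjusting the change contrast for age and sex.

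Because two models already failed to converge with sessions missed included, state a fallback: simplify the random effects, or keep sex-by-time only.

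The cost is a sentence or two and a refit. With three visits, each covariate adds two interaction parameters, so up to 2 + 2 = 4 more fixed effects per model with 61 participants. The SE will be slightly wider if gains do not differ by sex or age.
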